2.3.3 Safety Endpoints

1. Treatment-emergent Adverse Events (AEs)
2. Serious Adverse Events (SAEs)
3. Treatment-emergent Adverse Events leading to premature discontinuation of study drug/PK assessments
4. Clinical laboratory safety blood results
5. Changes in vital signs
6. Concomitant medications

3 STATISTICAL METHODOLOGY

3.1 General Considerations

All available data will be presented in subject data listings, which will be sorted by treatment sequence group, subject identifier and where appropriate, visit number and visit/assessment date.

Listings will contain data for all attended visits whether scheduled or unscheduled and visits will be listed in the order in which they were attended. Tables will summarize data for all attended visits.

Formulation / condition groups will be displayed in all output using the following labels:

- Ferric Maltol Capsule/Fed
- Ferric Maltol Suspension/Fed
- Ferric Maltol Capsule/Fasted

- Ferric Maltol Suspension/Fasted

Treatment sequence groups will be displayed in all output using the following labels:

- Ferric Maltol Sequence A
- Ferric Maltol Sequence B
- Ferric Maltol Sequence C
- Ferric Maltol Sequence D

3.1.1 *Other Data Handling Approaches*

In general, descriptive statistics (n, mean, standard deviation (SD), median, maximum and minimum) will be used to summarize the continuous data. Discrete measures will be summarized using counts and percentages (derived from the number of non-missing observations); the number of non-missing (n) observations will also be presented.

Unless otherwise stated, descriptive statistics showing the mean or median will be displayed to one more decimal place than the original data; the standard deviation will be displayed to two decimal places more than the original data and minimum and maximum values will be displayed to the same number of decimal places as the original data.

All fractional numeric values will be printed with a zero to the left of the decimal point (e.g., 0.12, 0.3 etc.). Percentage values will be printed with one digit to the right of the decimal point (e.g., 52.3%, 8.9% etc.).

3.1.2 *Analysis Day*

Analysis day will be calculated from the date of first dose of study drug. The day of the first dose of study drug will be Day 1, and the day immediately before Day 1 will be Day -1. There will be no Day 0.

3.1.3 *Handling of Dropouts and Missing Data*

All data will be used according to availability, with no imputation for missing data.

3.2 Baseline

Baseline is defined as reading or measurements at Day 1 prior to study drug administration of each period. If the reading at Day 1 predose is missing, the last reading before first dosing will be set as baseline.

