5.6 RISK-BENEFIT EVALUATION

The safety of Ferric Maltol in subjects with IDA and IBD has been established in a well-controlled Phase 3 clinical study with data having been collected over 12 weeks on 128 subjects in the double-blind phase and for over 12 months in some subjects in open-label follow-up (Gasche, 2015; Schmidt, 2016). The safety and tolerability of Ferric Maltol in adults with IDA in IBD study was positive, with the overall AE rate in Ferric Maltol being comparable to the Placebo group over a 12-week period; 87% of Ferric Maltol subjects remained in the study. This data is supported by smaller published clinical studies using higher doses of Ferric Maltol and by preclinical studies testing Ferric Maltol in rodents (see Investigator's Brochure).

The safety and tolerability study with Ferric Maltol in 167 subjects with CKD and IDA have been positive with data collected over 16 weeks in a double-blind phase. The TEAE was comparable between the active (70.1%) and placebo group (75%) with the most common system organ class of GI disorders. Only three subjects experienced study drug-related adverse events that led to discontinuation. Overall, Ferric Maltol resulted in clinically and statistically significant increase in Hb compared to placebo.

Previous Phase I PK study (ST10-01-101) was performed to describe the PK and iron uptake in 24 iron deficient subjects in three different dosing regimens (30, 60, 90 mg BID). The most commonly reported TEAEs (29.2%) were GI disorders which were consistent with the medical history of the subjects, who were recruited from specialist GI clinics. A single SAE was

reported which led to discontinuation of the study but was not considered to be related to study treatment.

The study population will recruit healthy subjects, male and female aged 18 and 55 yrs inclusive at the time of informed consent. All eligible subjects will enter a 4 Period treatment phase with 48 hrs washout between each dose administration. Subjects will either take a 30 mg ferric maltol as a capsule or 5 ml oral suspension according to the randomized sequences on each Period Day 1.

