10.6 VITAL SIGNS

Body temperature (°C), blood pressure and pulse rate will be assessed at Screening for all subjects on all four PK days at pre-dose. Blood pressure and pulse rate should be measured after the subject has been sitting for at least 5 minutes at Screening visit and at each PK days pre-dose.

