12.2 STATISTICAL METHODS

For each of serum iron, maltol, maltol glucuronide, TSAT, TIBC, UIBC and transferrin, concentration data will be listed for each individual subject, by formulation / condition. The concentration data will be summarized, for each formulation / condition, at each time point by using the following descriptive statistics: n (the number of subjects), arithmetic mean, standard deviation (SD), geometric mean, coefficient of variation (CV), median, minimum and maximum, and a 90% confidence interval (CI) for the mean.

Concentration-time courses of each component will be graphically displayed per subject. Plots of the geometric mean and its 90% CI, by formulation, will be provided, overlaid, for each condition separately.

For serum iron, baseline corrected serum iron, maltol, maltol glucuronide, TSAT, TIBC, UIBC and transferrin, PK parameters (C_{max} , T_{max} , AUC_{last} , AUC_{inf} , λ_z , $t_{1/2}$) will be calculated by non-compartmental analysis and listed by subject and by period. The parameters will be summarized, for each formulation / condition, by using the following descriptive statistics: n, arithmetic mean, SD, geometric mean, CV, median, minimum and maximum.

For each analyte, the within-subject ratios between capsule and suspension of C_{max} , AUC_{last} and AUC_{inf} will be also be calculated and listed per subject, for each of the fed and fasted conditions separately. These ratios will be summarized by n, geometric mean and a 90% confidence interval for the mean.

Other endpoints and safety data will be listed and summarized for each formulation.

Full details will be specified in the Analysis Plan prior to database lock.

All secondary endpoints will be summarized by formulation / condition:

1. Treatment-emergent Adverse Events (TEAEs)
2. Serious Adverse Events (SAEs)
3. Treatment-emergent Adverse Events leading to premature discontinuation of study drug/PK assessments
4. Routine clinical laboratory safety blood results
5. Changes in vital signs
6. Concomitant medications

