3.6.4 Vital Signs

Vital signs including blood pressure, pulse rate, temperature, and respiratory rate will be measured at Screening, Day -1, Day 1, Day 3, Day 5, Day 7, and Safety Follow-Up/ET. Height, weight, and body mass index (BMI) will be measured at Screening only.

Vital signs values and changes from baseline will be summarized at each scheduled visit by treatment sequence.

All vital signs data will be listed.

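### As written, the vital-sign change table does not give the change after each formulation / condition: the literal baseline rule makes every dosing-day change zero, and the table is by sequence

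*SAP*

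**What the plan says.** **Endpoint.** "Changes in vital signs" is a safety endpoint in SAP 2.3.3 and secondary endpoint 9 in Protocol 6.4. Protocol 6.2 names vital signs among the measures for the safety objective.

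**Baseline.** SAP 3.2 says: "Baseline is defined as reading or measurements at Day 1 prior to study drug administration of each period". Its next sentence is a fallback: "If the reading at Day 1 predose is missing, the last reading before first dosing will be set as baseline". SAP 3.1.2, on analysis day, says: "The day of the first dose of study drug will be Day 1". Protocol 5.6, by contrast, gives every period its own Day 1, since it describes dosing "according to the randomized sequences on each Period Day 1".

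**Timing and visits.** Protocol 10.6 takes vital signs at Screening and "on all four PK days at pre-dose". SAP 3.6.4 lists Screening, Day -1, Days 1, 3, 5 and 7, and the safety follow-up or early-termination visit. Footnote 2 of the schedule in Protocol 10.2 refers to treatment days and gives no time relative to dosing. Completers are followed up by telephone and early discontinuers at the clinic (Protocol 7.1).

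**Analysis.** SAP 3.6.4 plans: "Vital signs values and changes from baseline will be summarized at each scheduled visit by treatment sequence". Protocol 12.2 says: "All secondary endpoints will be summarized by formulation / condition", and its list under that statement includes changes in vital signs.

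**The concern.** A change from baseline is informative only if the later reading is a different measurement from the baseline and can be tied to the treatment in between. Taken together, the baseline rule, the pre-dose timing and the SAP visit list appear to set each dosing-day reading against itself. Grouping by sequence then removes the direct link to a formulation or feeding condition.

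At stake is one named, descriptive safety endpoint. Rows of zero change carry no information, and a table by sequence is not the summary the protocol promised. The primary PK comparison is not affected.

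**Working it through.** The plan gives no figure to reproduce here. The check is algebra on the visit list, followed by a count.

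**Inputs.** 32 subjects, 8 per sequence; doses on Days 1, 3, 5 and 7 (SAP 2.2.1, Table 1); one pre-dose reading on each dosing day (Protocol 10.6); visits from SAP 3.6.4. Write R1, R3, R5 and R7 for the four pre-dose readings. Change at a visit = reading at that visit minus baseline.

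**Step 1: the two possible baselines.**

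| SAP 3.6.4 visit | Period-specific baseline | First-dose baseline | Treatments given since the first-dose baseline |
|---|---|---|---|
| Day 1 | R1 - R1 = 0 | R1 - R1 = 0 | none |
| Day 3 | R3 - R3 = 0 | R3 - R1 | one |
| Day 5 | R5 - R5 = 0 | R5 - R1 | two |
| Day 7 | R7 - R7 = 0 | R7 - R1 | three |

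Screening and Day -1 precede any baseline. The follow-up visit yields a reading only for early discontinuers.

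Under the period-specific rule, 4 visits x 32 subjects = 128 planned changes, all exactly zero. If a period's pre-dose reading is missing, the fallback supplies a baseline, but that visit then has no reading to compare with it.

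Under the first-dose rule, Day 3 is a clean one-treatment change, while Days 5 and 7 accumulate two and three different treatments. The Day 7 dose has no later reading in the SAP list for completers.

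**Step 2: grouping.** Sequence and visit together identify the treatment just given, so a reader could rebuild the attribution by hand. The table itself would still spread each treatment over four sequences of 8 subjects and give no summary by formulation / condition.

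**Step 3: what the planned readings can give.** Use the next period's pre-dose reading minus the current period's pre-dose reading: R3 - R1, R5 - R3 and R7 - R5. The Period 4 treatments are:

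- Sequence A: suspension fasted
- Sequence B: capsule fasted
- Sequence C: suspension fed
- Sequence D: capsule fed

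Each treatment therefore falls in Period 4 for 8 subjects and in Periods 1 to 3 for 32 - 8 = 24. The total is 4 x 24 = 96 changes, each about 48 h after the dose. Period 4 contributes none.

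**Step 4: if further readings exist.** A Day 8 reading would be about 24 h after the Day 7 dose and would add 32 changes (8 per treatment), giving 96 + 32 = 128. The added 32 are at 24 h and the other 96 at 48 h. If readings are taken on Days 2, 4 and 6 as well as Day 8, all 128 changes (32 per treatment) are available at about 24 h.

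**The case against.** **The zeros depend on one of two readings of the baseline.** SAP 3.1.2 and the fallback sentence in 3.2 both point to the first dose, and a table by visit and sequence suits a single study-level baseline. This stands: a reader might infer that the table must be zero throughout, and the SAP does not force that. But the operative sentence in 3.2 refers to each period, and the first-dose reading has its own defects (Days 5 and 7, Period 4).

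**There may be more readings than SAP 3.6.4 lists.** The vital-signs row in the Protocol 10.2 schedule carries nine marks plus a bracketed one at follow-up, against six SAP visits before follow-up. The columns have collapsed in the text copy, so the three extra marks cannot be placed with certainty; washout days or Day 8 are plausible. SAP 2.2.1 refers to that schedule, and SAP 3.1 says tables cover all attended visits. Such readings would therefore be tabulated, with changes that are not zero by construction. This also stands. However, SAP 3.6.4 does not plan for them or attribute them to a treatment. Protocol 10.6 also does not expressly rule out other readings.

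**The endpoint is not beyond reach, and safety has another route.** A reader might conclude that it cannot be answered at all. The documents do not support that: the planned pre-dose readings suffice for a 48 h change, early discontinuers have a clinic visit, and observed values are summarised and listed. Clinically significant vital-sign findings must be reported as adverse events (Protocol 11.1.1), and SAP 3.6.2 tabulates treatment-emergent events by formulation / condition. The table specifications are in separate documents, so it is not known whether a change column is printed at the baseline visit. For the same reason, it is speculative that zeros would be misread as no effect.

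**Conclusion.** The point holds in a limited form. With the period-specific baseline taken literally, all 128 planned dosing-day changes are zero, and no later reading in the SAP list is compared with a completer's period baseline. With a first-dose baseline, three of the four dosing days give real changes, but only Day 3 isolates one treatment, and the Period 4 treatment is never followed by a listed reading. On both readings the grouping departs from Protocol 12.2. The analysis as written does not deliver the endpoint; the data for a 24 to 48 h answer are largely planned already.

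This rests on dosing-day readings being taken before the dose, as Protocol 10.6 says, and on SAP 3.6.4 being the operative visit list. No scheduled reading clearly supports a change within hours of dosing. The endpoint is descriptive and secondary, so the change is worth making before database lock but does not threaten the main conclusions.

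**What to change.** In SAP 3.2 and 3.6.4:

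1. State one vital-sign baseline: each period's pre-dose reading. Reword the fallback sentence to agree with it.
2. Define the period's change as the next scheduled reading after that dose minus that baseline. Use the washout-day or Day 8 reading if the schedule includes it, otherwise the next period's pre-dose reading.
3. Attribute the change to the treatment just given and summarise by formulation / condition.
4. Label each change with its actual post-dose time, about 24 h or about 48 h, and do not pool the two.
5. State that no scheduled reading clearly supports a change within hours of dosing, and that Period 4 contributes nothing unless a Day 8 reading exists.

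Reconcile the vital-sign days in the Protocol 10.2 schedule and its footnote 2, Protocol 10.6 and SAP 3.6.4.

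The cost is modest rework of SAP text and table shells, with no new measurement. The limitation that remains is that the change is measured 24 to 48 h after dosing.

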10.7 LABORATORY ASSESSMENTS

10.7.1 Hematology and Clinical Chemistry

Routine clinical laboratory safety bloods for hematology (3.0 mL) and clinical chemistry/iron markers (7.5 mL) evaluations will be collected at Screening to assess eligibility. Hematology (3 mL) and clinical chemistry (5.0 mL) will be repeated at Period 4; 24 hrs post-dose sampling or at the Follow-up visit for early discontinued subjects. Additional testing may be required if any abnormal value is reported and this must be followed until it is resolved.

All analyses will be conducted by a central laboratory. Procedures for the collection, processing, storing, and transporting of samples to the laboratory will be fully described in the study-specific Laboratory Manual.

Investigators will review, sign and date all lab results upon receipt from the central laboratory. If a value is flagged as outside of the normal range, the Investigator must document the abnormality as 'clinically significant' (CS) or 'non-clinically significant' (NCS). Any lab abnormality assessed as 'CS' must be recorded as an AE if not explained by a pre-existing condition (documented in the medical history).

The signed paper copy of the laboratory report is retained at the investigational site. The electronic data transferred from the central laboratory database to the clinical study database will be considered source data for the derivation of summary data and listings presented in the clinical study report.

10.7.1.1 *Hematology test parameters*

Red blood cell count, hemoglobin, hematocrit, white blood cell count (total and differential (% and absolute), absolute reticulocyte count and platelet count.

10.7.1.2 *Clinical Chemistry and Screening Iron Markers test parameters*

Clinical Chemistry: ALT, AST, alkaline phosphatase, gamma-glutamyl transpeptidase (GGT), total bilirubin, creatinine, blood urea nitrogen (BUN), sodium, potassium, chloride, calcium, total cholesterol, uric acid, glucose, total protein, albumin, bicarbonate, LDH, CK, triglycerides

Iron Markers: serum iron, transferrin, transferrin saturation (TSAT), total and unsaturated iron binding capacity (TIBC, UIBC).

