3.5 Pharmacokinetic Assessment

3.5.1 *PK blood sampling*

PK samples were to be collected on Day 1 to Day 8, pre-dose and post-dose according to the PK Sample Schedule Group that the subject was assigned to.

On all four PK study days, all subjects will have baseline PK blood samples collected immediately prior to Ferric Maltol dosing (0 hr). Subjects will then have further PK blood samples collected at 11 additional times after dosing; the post-dose PK sample times will be 15 mins \pm 2 min, 30 mins \pm 2 min, 45 mins \pm 5 min, 1 hr \pm 5 min, 1.5 hr \pm 5 min, 2 hrs \pm 5 min, 3 hrs \pm 5 min, 4 hrs \pm 5 min, 6 hr \pm 10 min, 10 hrs \pm 15 min and 24 hrs \pm 15 min.

For each individual subject, the post-dose PK blood sampling schedule will be the same on all four PK days. PK blood samples on the PK days will be: serum iron, total and unsaturated iron binding capacity (TIBC, UIBC), transferrin, transferrin saturation (TSAT), maltol and maltol glucuronide.

3.5.2 *Handling missing PK data or concentration below the lower limit of quantification*

If the actual sampling time is missing, but a valid concentration value has been measured, the concentration value will be flagged, and the scheduled time point may be used for the calculation of PK parameters. If the dosing history information for a subject is missing, the sampling for that subject relative to the missing dose will not be included in the analysis.

Missing concentrations related to serum iron, TSAT, transferrin, TIBC, and UIBC will not be imputed or used in the analysis. If the dosing history information for a patient is missing, the sampling for that patient relative to the missing dose will not be included in the analysis.

For maltol and maltol glucuronide, all drug concentration below the quantifiable limit (BQL) are treated as zero. When more than half (>50%) of the values at a single timepoint are BQL, mean and median values are reported as BQL. Standard deviation and %CV are not reported; maximum and minimum values are reported as observed (including BQL). If, as the result of the calculation (eg. dose normalization, descriptive statistics) a concentration value is less than the LLOQ the value should be reported as <LLOQ value. The following general rules will be applied for the concentration summary (including tabulation and plotting) for each period:

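### The SAP's fallback for a missing pre-dose value is tied to no period and conflicts with its own rule against imputing missing iron values

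*SAP*

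**What the plan says.** SAP 3.2 starts with a period-specific definition: "Baseline is defined as reading or measurements at Day 1 prior to study drug administration of each period". The next sentence gives the fallback: "If the reading at Day 1 predose is missing, the last reading before first dosing will be set as baseline". It does not say whether the first dosing meant is that of the study or of the period.

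Two other parts of the SAP deal with missing values. Section 3.1.3 is general: "All data will be used according to availability, with no imputation for missing data". Protocol 12.2.2 says the same. Section 3.5.2 is specific to the iron analytes: "Missing concentrations related to serum iron, TSAT, transferrin, TIBC, and UIBC will not be imputed or used in the analysis". Neither section makes an exception for baseline.

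A 0 hr sample is planned before dosing in all four periods (SAP 3.5.1). Serum iron is also measured at Screening (Protocol 10.7.1), within 14 days before Day 1. Baseline-corrected serum iron Cmax, AUClast and AUCinf are secondary endpoints (SAP 2.3.2). The primary endpoints are Cmax and AUClast of total serum iron (SAP 2.3.1). Neither document gives the formula for baseline-corrected iron or says which baseline it uses.

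**The concern.** A baseline correction is meant to remove the iron level at which the subject enters that period. The fallback can supply a value from another time, in Periods 2–4 from before one, two or three iron doses. One wrong baseline carries into every post-dose value of that subject's period, and so into that subject's suspension/capsule ratio.

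The SAP also gives two instructions for the same event. Under 3.5.2 a missing 0 hr iron value is not imputed. Under 3.2 another reading takes its place. SAP 3.5.5 admits a subject to a comparison only if the parameter is calculable for both formulations, so the choice of rule also decides whether the subject is in the analysis. A period with no valid baseline would look calculable under 3.2.

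**Working it through.** **Step 1. What the fallback can mean.** SAP Table 1 puts dosing on Days 1, 3, 5 and 7.

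| Reading | Period 1 value missing | Period 2, 3 or 4 value missing |
|---|---|---|
| First dosing is the first dose of the study | Screening | Period 1 pre-dose value, 3 − 1 = 2, 5 − 1 = 4 or 7 − 1 = 6 days old; failing that, Screening |
| Day 1 is used as in SAP 3.1.2 | Screening | No fallback |
| First dosing is the dose of that period | Screening | Previous period's 24 h post-dose sample |

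The first reading is the most natural. Each period has a single dose, so the word first adds little within a period, and SAP 3.1.2 uses the corresponding phrase for the start of the study. The second reading follows from that section's definition: "The day of the first dose of study drug will be Day 1". Against it, the opening sentence of 3.2 speaks of a Day 1 in each period, and Protocol 5.6 also has subjects dosed "according to the randomized sequences on each Period Day 1". The third reading is possible but strained.

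**Step 2. Conflict with the missing-data rules.** Under each reading at least one case puts another reading in place of a missing 0 hr iron value. SAP 3.5.2 excludes this directly and 3.1.3 excludes it in general.

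**Step 3. Effect in an affected subject-period.** This assumes that the correction subtracts the 3.2 baseline. Let B be the true pre-dose value and B + d the substitute. Each corrected value becomes C(t) − B − d. Then:

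- corrected Cmax changes by −d;
- corrected AUC over 24 h changes by about −24d. This is approximate because SAP 3.5.4 uses the linear-up log-down rule;
- corrected AUCinf changes further, because the terminal slope is fitted to the logarithms of the shifted values.

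As a share of the true value, the Cmax error is r = d/Cmax. If the mean corrected concentration over 24 h is a × Cmax, the AUC error is r/a. The documents give no iron values, so a and r are assumed. With r = 0.10, the AUC error is 0.10/0.5 = 20% for a = 0.5 and 0.10/0.2 = 50% for a = 0.2. With r = 0.25 and a = 0.2 it is 0.25/0.2 = 125%.

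**Step 4. Effect on the overall ratio.** The planned number is 32 (SAP 2.2.1). Suppose that k subjects have the same error e (as a share of the true parameter; positive if the baseline is too high), in one formulation only. With equal weights, the geometric mean ratio is multiplied by (1 − e)^(k/32).

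| Assumed error e | Subject's parameter × | Overall ratio ×, k = 1 | Overall ratio ×, k = 4 |
|---|---|---|---|
| +50% | 0.50 | 0.979 | 0.917 |
| +25% | 0.75 | 0.991 | 0.965 |
| −25% | 1.25 | 1.007 | 1.028 |
| −50% | 1.50 | 1.013 | 1.052 |
| −125% | 2.25 | 1.026 | 1.107 |

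The last row is the extreme AUC case of Step 3: 2.25^(1/32) = 1.026 and 2.25^(4/32) = 1.107. An error of +100% or more makes the corrected parameter zero or negative. It then has no logarithm and drops out of the model in SAP 3.5.5.

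**Step 5. Primary endpoints.** Total-iron Cmax and AUClast have no baseline subtracted, so the fallback does not change them.

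**The case against.** The best defence is that 3.2 is a general section that also serves the safety data. Safety laboratory samples are taken only at Screening and Day 8 or early termination (SAP 3.6.3), so they have no Day 1 pre-dose reading, and the fallback is what gives them a baseline. For PK iron, the specific rule in 3.5.2 can be read as overriding the general one, which would give nearly the result proposed below. The fallback does have this legitimate use. But the SAP does not state which section takes precedence, and 3.2 is its only definition of baseline, so a programmer could follow it for corrected iron.

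Exposure is also narrow. Subjects stay in the unit, dosing under fasted conditions follows the 0 hr sample, and each iron sample is split into two aliquots (Protocol 8.3.1 and 10.7.2). Missing pre-dose values may be few, though the documents give no expected rate. This limits the effect but does not reconcile the two rules.

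A reader might infer that the SAP plainly orders a reading from before the study's first dose for Periods 2–4, and so corrupts baseline-corrected iron in those periods. The documents do not support that. The words tying the fallback to the study's first dose are absent, and SAP 3.1.2 allows a reading confined to Period 1. The link from 3.2 to the correction is likely but unstated. Nothing happens unless a pre-dose value is missing, and Period 1 is exposed too.

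**Conclusion.** The fallback in SAP 3.2 is not period-specific and conflicts with 3.5.2 and 3.1.3 whenever it is used for an iron value. That holds under each reading in Step 1.

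The numerical effect is conditional. It needs a missing 0 hr value, a correction that subtracts the 3.2 baseline, and a substitute that differs from the true value. The distortion in one subject-period can then be large. For one affected subject of 32, the overall Cmax ratio moves by about 1–2% even at assumed errors of 50%. With four affected in the same direction, the factor is 0.917 to 1.052. AUC is more sensitive for the same baseline error. Large percentage errors for a single subject-period should not be read as errors in the trial's result: they rest on assumed inputs, and the documents give neither the drift in serum iron between periods nor the rate of missing samples.

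Only secondary endpoints are touched. The point is worth correcting because the contradiction is in the text and is easily removed.

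**What to change.** In SAP 3.2, before database lock:

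- state the formula for baseline-corrected serum iron, and that it uses the 0 hr value of the same period;
- state that, if this value is missing, baseline-corrected parameters are not calculated for that subject and period;
- limit the fallback to safety variables, worded as the last reading before that period's dose, which is Screening for the safety laboratory tests.

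This brings 3.2 into line with 3.5.2 and 3.1.3. The cost is a few lines of text. Because SAP 3.5.5 requires both formulations, an affected subject also loses the capsule/suspension pair for that condition in the secondary analysis of baseline-corrected iron, not just one value. The other condition's pair remains.
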